8. STATISTICAL METHODS

The retrospective eMR audit does not require a power calculation as we are not testing an intervention but seeking to explore and characterise service data. Phase 1 data to be collected includes: patient demographic information (age, gender, etc.) and clinical information (for example date/time of arrival, triage category, reason for ED presentation, assessment and diagnostic code, discharge summary, nursing documentation, community referrals, length of stay, disposition, ED clinical space) to determine patients that have presented or discharged with signs/symptoms of head injury or concussion pre COVID 19 and during the pandemic.

For the descriptive exploratory study quantitative data will be presented using descriptive statistics and summarised using frequencies and percentages. Examining for central tendency means, standard deviation (normally distributed data), or median and interquartile range (non-normally distributed data) will be analysed. For continuous data comparison will be conducted using T test and Chi square will be used for categorical data. If the data allows (there are sufficient observations and the distribution of data is appropriate) we will conduct multivariate analyses to explore the determinants of patient compliance with ED discharge information. Quantitative data analysis will be performed using SPSS v.21 and Excel for data cleaning, mining and summaries of data sets. All data will be de-identified.

For Phase 2 involves qualitative interview data obtained from semi-structured telephone interviews. Data to be collected includes: patient demographic information (age, gender, etc.), history including mechanism of injury, signs/ symptoms of concussion, management in ED and follow up plan. All responses provided by patients or their persons responsible will be analysed and organised thematically and stored and managed using NVivo™ v12. Thematic analysis will be guided by Gibbs's (2007) framework which includes: 1) transcription and familiarisation; 2) code building; 3) dis/confirmatory theme development; and 4) data consolidation and interpretation. This framework provides a systematic approach for interpretation (Lichtman, 2010, Brodie and Irving, 2007). The investigators will discuss and review emerging coding and themes.

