Characteristics, patterns and outcomes of patients who present with head injuries to one tertiary emergency department: multi-method study

CONFIDENTIAL

This document is confidential and the property of Royal North Shore Hospital Northern Sydney Local Health District

No part of it may be transmitted, reproduced, published, or used without prior written authorisation from the Institution.

STATEMENT OF COMPLIANCE

This document is a protocol for a clinical research study. The study will be conducted in compliance with all stipulations of this protocol, the conditions of ethics committee approval, the NHMRC National Statement on Ethical Conduct in Human Research (2007) and the Note for Guidance on Good Clinical Practice (CPMP/ICH-135/95)

PROTOCOL SYNOPSIS

Title	Characteristics, patterns and outcomes of head injuries presenting to one tertiary emergency department (ED).
Objectives	
Primary: the incidence of patient presentations to Royal North Shore Hospital (RNSH) ED with head injury.
 
Secondary: to follow up on patient journey at 10-14 days and four weeks from discharge. To review; the discharge process from ED, patient symptoms/progress, community management and the need for further management.

Study Design	Observational Cohort Study
Planned Sample Size	
Phase 1 medical record audit: 36 months (2019/2020/2021) of electronic medical record (eMR) data ~267,000 patients.
 
Phase 2 telephone interview: anticipate recruitment rate of 150 patients.

Selection Criteria	
Phase1: what is the incidence of head injuries and does the pandemic and social isolation impact or change the rate of presentations to ED?
 
Phase 2: patients up to 30 years of age who present to the ED with a head injury then discharged home or admitted to the ward.

Study Procedures	
Identify suitable patients on presentation to ED, review eMR diagnosis/documentation, fill excel data spreadsheet, two follow up phone call interviews (at 10-14 days and four weeks from day of discharge). Qualitative study, data collection including a retrospective record review.
 
Phase 1: retrospective 36 month eMR audit to examine the incidence, characteristics and patterns of patients that present with a head injury before and during the Covid-19 pandemic.
 
Phase 2: telephone follow up of patients (up to 30 years of age) that present to the ED with a head injury and discharged home or admitted to the ward.

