1.3 Statistician (if applicable)

Mainly descriptive exploratory data will be presented and summarised using frequencies and percentages. Basic inferential statistics will be used for group comparisons to be undertaken depending on data distribution. Normally distributed data will be analysed using t test and anova. Non normally distributed data will use parametric testing Mann Whitney, Kruskal Wallis, Chi Square and Fischer exact depending on data type and coding.

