2.2 Research Question

Phase 1: Primary question: What are the characteristics, patterns and outcomes of people (up to 30 years of age) that present with signs and symptoms of head injuries to one major tertiary referral hospital ED and does the COVID-19 pandemic and social isolation impact on or change the presentation rate for patients with head injuries?

Phase 2: To follow up on a patient's health trajectory journey at 10-14 days and then four weeks post discharge. Follow up will involve exploring the discharge processes, patient symptoms/progress, community management and follow up with a community practitioner.

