4.6 Primary and Secondary Outcome Measures

Primary outcome:

- To explore the characteristics, patterns and outcomes of patients that present with head injuries to one major tertiary referral hospital ED.
- How are head injury patients managed in the community and the need for further management.

Secondary outcomes:

- To compare data both pre and during the COVID-19 pandemic
- Identification of evidence based concussion assessment and management in the ED
- How were head injury patients managed in the ED
- Identification of the type and appropriateness of discharge information, education and instructions
- What discharge instructions were provided for commencing post head injury activities such as return to school, work and sporting activities
- What were the patterns of community referrals

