All patients will have the opportunity to opt out of the study without any impact on care practices. Randomisation will occur 1:1 ratio for patients < 16 years of age and patients > 16 years of age to identify 20 participants per week, who will be contacted 10-14 days post injury and then four weeks post discharge. Telephone interviews will be conducted by either ED research volunteers, the lead researcher or associate researchers from the RNSH ED Office. Prior to the commencement of the telephone interview each patient/parent/carer on contact will be again given the opportunity to opt out and verbal consent will be obtained. Each participant will be invited to select an interview schedule time suitable for them. Potential participants will only be contacted three times and if unable to be contacted will be considered as declining to participate in the study. Potential participants will only be contacted between the hours of 0800am until 0600pm (Monday – Friday).

All emergency clinicians will be briefed about the study via email, posters and short in-services.

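### The protocol asks whether the pandemic changed the head-injury presentation rate, but defines neither the rate nor the pre/during date and names only unadjusted tests that do not model a rate over time

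*Protocol*

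**What the plan says.** The question is about a rate. Protocol section 2.2 asks, as part of the Phase 1 primary question, "does the COVID-19 pandemic and social isolation impact on or change the presentation rate for patients with head injuries". The Selection Criteria row of the synopsis asks "what is the incidence of head injuries and does the pandemic and social isolation impact or change the rate of presentations to ED". Section 4.6 lists the comparison among the secondary outcomes: "To compare data both pre and during the COVID-19 pandemic".

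The comparative methods appear in two places:

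- Section 8: "For continuous data comparison will be conducted using T test and Chi square will be used for categorical data".
- Section 1.3: "Normally distributed data will be analysed using t test and anova", followed by "Non normally distributed data will use parametric testing Mann Whitney, Kruskal Wallis, Chi Square and Fischer exact depending on data type and coding".

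The only adjusted analysis concerns something else: "we will conduct multivariate analyses to explore the determinants of patient compliance with ED discharge information". Section 8.2, although headed as the statistical analysis plan, adds only frequencies and central tendency.

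The audit window is 1 January 2019 to 31 December 2021. No section gives the date that divides the period before the pandemic from the period during it. No section says what the numerator and denominator of the rate are.

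**The concern.** A before/during comparison of a presentation rate needs three things fixed: what is counted, per what, and from which date. The protocol fixes none of them. The tests it lists suit comparisons of patient characteristics.

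Applied to head injury yes/no among ED presentations, a chi-square tests the share of ED workload that is head injury. The share equals the rate only up to total ED volume. If total volume moves, share and rate can part company, and with thousands of cases either can be highly significant while the other is flat. With no start date, it is also open whether the two periods cover the same months of the year.

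At stake is the conclusion on the pandemic question. Two analysts following the protocol faithfully could report opposite answers, and the choice could be made after the data are seen.

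There is also a smaller inconsistency. Section 1.3 sends non-normal data to rank tests (and calls them parametric), while section 8 sends all continuous comparisons to a t test.

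**Working it through.** **Inputs from the protocol.** About 89,000 ED presentations a year, 5% of them head injury (synopsis; section 4.3); 36 months of records, about 267,000 (sections 4.3 and 8.1).

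**The protocol's own figures.** 3 × 89,000 = 267,000, which reproduces. 5% × 89,000 = 4,450, which reproduces as a figure for one year; 36 months would give 5% × 267,000 = 13,350. Both are totals before restriction to patients up to 30. No alpha, power or effect size is stated for the rate question, so there is no power figure to reproduce.

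**Assumptions, not in the documents.** Split of 12/24, 14/22 or 15/21 months; ED volume during the pandemic lower by 5%, 10% or 20%; seasonal amplitude of 10% to 30% with a mid-year peak.

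**1. Share against rate, 12/24 split, 10% fall.** Before: 4,450 of 89,000, a share of 5.00%.

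*Head injuries per month unchanged, volume down 10%.* During: 8,900 of 2 × 0.9 × 89,000 = 160,200, a share of 5.56%.

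- Share test: pooled proportion 13,350/249,200 = 0.05357. SE = √[0.05357 × 0.94643 × (1/89,000 + 1/160,200)] = 0.000941. Chi-square = (0.005556/0.000941)² = 34.8, p = 3.6e-9.
- Rate ratio = (8,900/24)/(4,450/12) = 1.00. 95% CI = exp(0 ± 1.96 × √(1/4,450 + 1/8,900)) = 0.96 to 1.04.

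*Both down 10%.* During: 8,010 of 160,200, a share of 5.00%.

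- Share test: chi-square = 0, p = 1.
- Rate ratio = (8,010/24)/(4,450/12) = 0.90. 95% CI = exp(ln 0.90 ± 1.96 × √(1/4,450 + 1/8,010)) = 0.87 to 0.93.

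Over the assumed range:

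| Fall in volume | Head injuries unchanged: share during; share-test p; rate ratio | Both fall equally: share-test p; rate ratio (95% CI) |
|---|---|---|
| 5% | 5.26%; 0.004; 1.00 | 1; 0.95 (0.92–0.99) |
| 10% | 5.56%; 3.6e-9; 1.00 | 1; 0.90 (0.87–0.93) |
| 20% | 6.25%; 4e-36; 1.00 | 1; 0.80 (0.77–0.83) |

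The 14/22 and 15/21 splits give the same picture (chi-square 37.2 and 38.1 for the 10% fall with head injuries unchanged).

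**2. Season, no pandemic effect.** Simulation of 36 monthly Poisson head-injury counts with mean 4,450/12 × [1 + s·cos(2π(m − 6)/12)], where m = 0 is January. Total volume is held constant, with 1,000 runs per cell. Proportion of runs in which the share test gives p < 0.05:

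| Amplitude s | 12/24 | 14/22 | 15/21 |
|---|---|---|---|
| 10% | 5.5% | 22.9% | 33.1% |
| 20% | 6.6% | 68.0% | 86.4% |
| 30% | 5.8% | 96.9% | 99.6% |

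Whole calendar years balance a fixed season; a cut within the year does not.

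**3. A t test on the 36 monthly counts.** It does not over-reject (at most 3.6% of runs), but unmodelled season inflates its error term. Power to detect a true 10% fall is 84% to 99% at 10% amplitude, 0.3% to 41% at 20%, and 0.2% or less at 30%, depending on the split.

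**The case against.** The strongest reply is that the protocol describes itself as descriptive and exploratory, lists the pandemic comparison as secondary in section 4.6, and need not set out offsets and month terms that a separate SAP may hold. It also fixes no unit of analysis, so monthly counts could be compared with the listed tests. And its only numerical statement of head-injury frequency is a share, 5% of presentations, so the share may be what is meant. Much of this is fair. It does not remove the point: section 2.2 places the comparison in the primary question, the protocol does name its comparative methods, and nothing says which meaning of rate they apply to or from what date.

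Several stronger readings are tempting and not supported:

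- A reader might infer that the listed tests cannot answer the question at all. They can give a crude answer, either as a share test or as a t test on monthly counts.
- A reader might infer that ED volume did change. The protocol plans on a constant 89,000 a year; the falls above are illustrations.
- A reader might infer that unequal periods or season bias every version. Period length cancels in a share or in monthly counts, and whole calendar years balance a fixed season.
- A reader might infer that Phase 2 contaminates 2021, because "All emergency clinicians will be briefed about the study via email, posters and short in-services". This is possible but not shown. Under section 5.1 the lead researcher reviews the records of all presentations, and the 2021 records are accessed retrospectively. No briefing date is given, so 2020 is not shown to precede the briefings, and restricting the main contrast to 2020 is not justified on this ground.

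**Conclusion.** The point holds in this form: the named methods are unadjusted and do not model a rate over time, and the protocol leaves undefined both the rate and the date that divides the two periods. On the protocol's own planning figures, an assumed 10% change in ED volume is enough for share and rate to give opposite conclusions (p = 3.6e-9 against a ratio of 1.00, or p = 1 against a ratio of 0.90). With a within-year cut and no pandemic effect, the share test rejected in 23% to over 99% of runs across the assumed seasonal amplitudes.

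These sizes rest on assumed volume changes, splits and seasonal patterns, on all-age totals where the question concerns patients up to 30, and on Poisson variation. Real intervals will be wider. They show that the choice matters, not that any particular result will occur. Neither the share nor the count is wrong in itself; the defect is that the protocol does not choose.

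**What to change.** 1. State the calendar date on which the pandemic period begins.
2. Define the rate for this question as monthly head-injury presentations in patients up to 30. Analyse it by negative binomial or overdispersed Poisson regression with a days-in-month offset, calendar-month terms and a pandemic-period term, and report a rate ratio with 95% CI. 2020 and 2021 may also be shown separately.
3. Report head injury as a share of ED presentations in the same age group as a separate, named estimand.
4. Keep the t, rank, chi-square and Fisher tests for patient characteristics. Align section 8 with section 1.3 so that skewed continuous variables such as length of stay use rank tests, and correct the word parametric in section 1.3.

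The cost is a few lines of protocol text and one extra regression. Arrival date and time are already collected (section 8), and all presentations up to 30 are already reviewed (sections 5.1 and 5.2.1), so both the counts and the denominator exist. The downside is a somewhat wider interval from overdispersion and the month terms. The change should be made before the two periods are compared.

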8.1 Sample Size Estimation

This is an observational study not requiring a powered sample.

Phase 1 medical record audit: 36 months of ED data characterising approximately 267,000 patients. All data is routinely collected and will be obtained through eMR

Phase 2 telephone interview: anticipate recruitment rate 280 patients or until data saturation is reached.

8.2 Statistical Analysis Plan

We will conduct measures of frequency and central tendency to analyse the collected data set. Incomplete data sets will not be used in our statistical analysis. We will report the number of incomplete data sets collected.

9. DATA MANAGEMENT

Phase 1 and Phase 2: All electronic data will be de-identified and stored using REDCap (on the NSLHD server) accessible by the lead researcher and other associate investigators. All paper data will be stored in a locked filing cabinet within the RNSH ED Office only accessible by the lead researcher. Phase 1: Data will be accessed as an eMR audit and will only contain de-identified records to enable the exploration for all potential ED head injury presentations.

Phase 2 data an electronic (Excel) master copy of codes for patient data will be stored using REDCap (on the NSLHD server) and will only be accessible by the lead researcher. All data will be de-identified so that there is no personal data collected (e.g. medical record number and name will not be collected) for the interviews. Instead patient participants will be allocated a unique identifier (study number) to ensure confidentiality, privacy and beneficence and ensure accuracy during data analysis. Phase 2: All interview paper forms / data will be kept in a locked filing cabinet within the RNSH ED Office only accessible by the lead researcher. Any paper notes taken by the investigators will be shredded using an industrial grade shredder located at the conclusion of the study. Data will be aggregated for analysis and publications will not contain any information that may identify an individual participant.

9.1 Data Storage

Phase 1: all electronic data will be coded to protect patient privacy on password protected excel sheet stored using REDCap (on the NSLHD server). Only the lead investigator will have access to the data source and database and will keep the password safeguarded.

Phase 2: all paper forms and data will be kept in locked filing cabinet within the RNSH ED Office only accessible by the lead investigator. All electronic data will be re-coded to protect patient privacy. Only the lead investigator will have access to the patient data and the telephone database and will be kept stored using REDCap (on the NSLHD server) only accessible to the lead investigator.

9.2 Data confidentiality

Phase 1 medical record audit: On extraction of first data patients will only be temporarily identified to establish representation rate then all patients will be coded and de-identified.

Phase 2 telephone interview: There is low risk for participants completing the telephone survey. No identifying personal data will be documented on the survey which will therefore remain anonymous to ensure confidentiality, privacy and beneficence. It will be communicated to the participants that they can exit from the interview at any time.

9.3 Study Record Retention

All records will be retained for a minimum of 5 years post study completion or last publication.

10. ADMINISTRATIVE ASPECTS

10.1 Independent HREC approval

The study has only been submitted to the Northern Sydney Local Health District HREC, reference number:

10.2 Amendments to the protocol

Any amendments will be submitted to the NSLHD HREC for review prior to implementation as per HREC guidelines.

10.3 Participant reimbursement

There are no reimbursements as this is an unfunded study.

10.4 Financial disclosure and conflicts of interest

The research team have no financial conflict of interest to disclose.

11. USE OF DATA AND PUBLICATIONS POLICY

The results of the study would lead to peer reviewed journal publications and conference presentations. We anticipate the findings of this study will lead to policy change for discharge and care practices. In addition the findings will contribute to the education programs for clinicians in the ED. Other changes anticipated would be the identification of gaps or issues pertaining to community care.

